# 9.7.3 Assessment of cleaved NOTCH1 protein levels in archival tumor material

If available, archival tumor material (FFPE sections) may be analyzed by immunohistochemistry to assess protein levels of cleaved NOTCH1 protein. Analyses will be performed centrally. Resulting data will be reported separately.

### 9.7.4 Evaluation of additional mutations

Information about additional mutations in tumor material will be collected if available. While patient eligibility is conditional to the *NOTCH1* loss-of-function status of their disease, other

mutations may be present which could alter response to bimiralisib. Based upon TCGA data, we expect several other alterations detectable by the Foundation One platform to occur with *NOTCH1* mutations at a reasonable prevalence, including mutations in TP53, FAT1, CDKN2A, PIK3CA, KMT2D, and Cyclin D amplifications. However, based upon their frequency of cooccurrence and power calculations, we do not expect to have sufficient power to detect their effects unless either the mutated or wild type groups have response rates approaching 70%, with response rates < 20% in the opposite group. Still, we will analyze the data for exploratory purpose and trends could be tested in future clinical trials. Resulting data will be reported separately.

# 9.8 Treatment period

Patients will receive bimiralisib until unacceptable AE, disease progression (radiologically documented as per RECIST version 1.1 [2, 3]), patient's request for withdrawal, investigator judgement or death – whichever comes first.

# 9.9 End of treatment (EOT)

Patients who discontinue bimiralisib should be scheduled for an End of Treatment (EOT) visit within 7 days of the decision of study discontinuation. For details of EOT assessments, refer to the table of assessments (Table 2). If the decision to withdraw the patient occurs at a regularly scheduled visit, that visit may become the EOT.

# 9.10 Patient withdrawal

Patients may voluntarily withdraw from the study or be removed from it at the discretion of the investigator at any time. Premature patient withdrawal refers to the point/time when the patient voluntarily discontinues study treatment. At the time of withdrawal, all study procedures outlined for the End of Treatment visit should be completed. Should a patient request or decide to withdraw, all efforts should be made to complete and report the observations as thoroughly as possible up to the date of withdrawal.

All information should be reported on the applicable CRFs. The investigator (or designee) must notify PIQUR of the patient's treatment discontinuation.

Patient must be withdrawn from the study treatment if any of the following occur:

- Pregnancy
- Progressive disease
- Unacceptable adverse event
- Lost to follow-up
- Physician decision

- Study terminated by sponsor
- Patient decision
- Patient unable to attend two (2) or more protocol-specified study visits due to COVID-19

Patients may be withdrawn from the study treatment if any of the following occur:

- Non-compliance with study treatment
- Protocol deviation

# 9.11 Patient Replacement

If patients withdraw consent or drop out for other reasons unrelated to safety or disease progression, they may be replaced. This includes patients who start smoking (as evidenced by cotinine test) within the first 12 weeks on bimiralisib treatment. These patients may remain on treatment but will be replaced. Patients who start smoking after the first 12 weeks on bimiralisib treatment will not be replaced. Patients for whom IHC analyses indicate high protein levels of NICD which are deemed incompatible with NOTCH1 loss-of-function may be replaced.

In total, we anticipate up to 20% of patients to drop out, resulting in enrollment of up to 35 patients in total.

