# **10.1** Statistical hypotheses

This is an open-label, single arm, two-stage study evaluating clinical efficacy, safety and pharmacokinetics of bimiralisib in patients with recurrent or metastatic HNSCC harboring *NOTCH1* LOF mutations. The primary goal of the clinical trial is to determine the objective response rate (ORR, including confirmed complete and partial responses) in patients with r/m HNSCC harboring *NOTCH1* to oral bimiralisib. An ORR of 10% or less is considered to be uninteresting and therefore this study has been designed with a reasonable power to detect a response rate of 30%.

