# **10.2** Sample size determination

To minimize accrual if bimiralisib is ineffective, a Simon's optimal two-stage design is used. In order to have 80% power to detect a response rate of 30%, (one-sided  $\alpha$ =0.05 and  $\beta$ =0.20) up to 10 patients will be enrolled in the first stage. If 1 or 0 patient respond to the treatment, the trial will be closed due to futility and the treatment is considered ineffective. If two or more patients have an objective response, the study will enroll an additional 19 patients in the second stage. The null hypothesis (H0: ORR  $\leq$  10%) will be rejected if the number of responses is  $\geq$  6 in 29 patients.

If patients withdraw consent or drop out for other reasons unrelated to safety or disease progression, they may be replaced (see section 9.11). We anticipate up to 20% of patients to drop out, resulting in enrollment of up to 35 patients in total.

This sample size is also reasonable to evaluate the pharmacokinetic and other correlative science endpoints; yet, no explicit sample size justification is made for these exploratory endpoints.

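### The general replacement rule has no time limit and no response condition, so replacing patients already scanned without a response can push the type I error above the stated 0.05

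*Protocol*

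**What the plan says.** Protocol 9.11 gives the general route: "If patients withdraw consent or drop out for other reasons unrelated to safety or disease progression, they may be replaced". Sections 4.1 and 10.2 and SAP 1.2 repeat it. The wording is permissive, has no time window and does not mention response status.

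Two narrower routes do have limits. On new smokers, 9.11 says: "Patients who start smoking after the first 12 weeks on bimiralisib treatment will not be replaced". Section 7.2 allows replacement of patients who cannot restart at the reduced dose, but only during the first three months. A further route, for high NICD levels, appears in 4.1 and 9.11.

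Reasons for leaving are listed in 9.10. Some require withdrawal, including patient decision, physician decision and loss to follow-up. A second list, introduced by "Patients may be withdrawn from the study treatment if any of the following occur", covers non-compliance and protocol deviation.

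On-treatment scans fall at Day 43, Day 85 and every 6 weeks after that (9.3, Table 2). Stage 1 response is evaluated on an ongoing basis (4.1). The principal investigator and the sponsor review tumour response at least every two months (12.1.8).

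Section 10.2 states that the null hypothesis "will be rejected if the number of responses is" 6 or more in 29, and expects up to 35 enrolled. Efficacy is analysed on the per-protocol set (10.4.1). Exclusions from that set are deferred to the data handling plan and the SAP (10.3.2). The available SAP text does not list them or say how a replaced patient counts.

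**The concern.** A two-stage binomial rule keeps its error rates only if the patients who count are fixed without reference to their outcome. Here those who decide on a replacement can already know that the patient has been scanned and has not responded. A patient with a confirmed response has less reason to leave than one without. If replaced patients drop out of the denominator, each swap of a non-responder gives the drug another chance at a response within a fixed 29.

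Both decisions are exposed: 2 of 10 opens stage 2, and 6 of 29 rejects the null. The reported ORR would be biased upwards as well. Nothing in the available text works as a check: replacement decisions need not be made without knowledge of scan results, and no ORR in all treated patients is planned.

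**Working it through.** **Inputs from the documents.** Null ORR 10% (10.1: "An ORR of 10% or less is considered to be uninteresting"). Target 30% (10.2: "In order to have 80% power to detect a response rate of 30"%). One-sided alpha 0.05. Stage 1 has 10 patients and continues with 2 or more responses; stage 2 has 19; reject at 6 or more of 29. Anticipated maximum enrolment is 35, so 35 − 29 = 6 replacements.

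**Assumptions.** Replaced patients leave the 29. The leaving rates below are not in the documents and are shown as a range.

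**Step 1: the plan's own figures.** P(reject) = Σ over x = 2 to 10 of Bin(x; 10, p) × P[Bin(19, p) ≥ 6 − x]. At p = 0.10:

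| Stage 1 responses | Probability | P(enough in stage 2) | Product |
|---|---|---|---|
| 2 | 0.1937 | 0.1150 | 0.0223 |
| 3 | 0.0574 | 0.2946 | 0.0169 |
| 4 | 0.0112 | 0.5797 | 0.0065 |
| 5 | 0.0015 | 0.8649 | 0.0013 |
| 6 or more | 0.0001 | 1 | 0.0001 |

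The sum is 0.0471. At p = 0.30 the same formula gives power 0.805. The design is reproduced.

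**Step 2: a fixed number of swapped non-responders.** Removing k1 non-responders in stage 1 and k2 in stage 2, and enrolling as many again, leaves the response count as if 10 + k1 and 19 + k2 patients had been treated. The cut-offs stay at 2 and 6. At p = 0.10:

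| Swaps | Stage sizes in formula | Type I error | P(opening stage 2) |
|---|---|---|---|
| None | 10 + 19 | 0.0471 | 0.264 |
| 1 in stage 2 | 10 + 20 | 0.0525 | 0.264 |
| 1 in stage 1 | 11 + 19 | 0.0570 | 0.303 |
| 3 in stage 2 | 10 + 22 | 0.0640 | 0.264 |
| 3 in stage 1 | 13 + 19 | 0.0793 | 0.379 |
| 6 in stage 2 | 10 + 25 | 0.0820 | 0.264 |
| 6 in stage 1 | 16 + 19 | 0.1184 | 0.485 |

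**Step 3: swaps at random.** Let each non-responder leave and be replaced with probability q, and each responder with probability cq. Newcomers follow the same rule. Without a cap, the chance that a place ends with a responder is p(1 − cq) / [p(1 − cq) + (1 − p)(1 − q)]. For c = 0 and q = 0.10 this is 0.10 / (0.10 + 0.90 × 0.90) = 0.1099, and putting it into the Step 1 formula gives 6.8%. With a total of six replacements, I filled the 29 places one by one and used up one replacement at each swap (exact recursion):

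| q | No responder leaves (c = 0) | Responders leave half as often (c = ½) | Equal leaving (c = 1) |
|---|---|---|---|
| 5% | 5.7% | 5.2% | 4.7% |
| 10% | 6.8% | 5.7% | 4.7% |
| 20% | 9.1% | 6.6% (7.1% without the cap) | 4.7% |

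**The case against.** Four objections carry weight.

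- **Size.** The larger figures need no responder to leave, every eligible non-responder to be replaced although the rule is optional, and all six extra places to go to this route. New smokers, NICD cases and the 7.2 cases may use the same places. With three places and q = 20%, the recursion gives 7.3%, or 5.9% if responders leave half as often. Exits for progression or safety are outside the route, so q may be small. This stands: the size is conditional.
- **Denominator.** No sentence says that a replaced patient leaves the 29. This also stands. It is inferred from a fixed 29 beside enrolment of up to 35, and the available text does not settle it.
- **Stable disease.** A reader might infer that stable disease at Days 43 and 85 is a completed negative result. Section 9.3 does not support that, because a response may first appear and be confirmed later. A patient who leaves then has been assessed without a response, which is all this point needs.
- **Clinical deterioration.** Section 9.8 describes progression as "disease progression (radiologically documented as per RECIST version 1.1 [2, 3])", so a reader might infer that anyone who worsens and leaves before a scan is replaceable. The documents largely close that path. Section 9.10 asks for End of Treatment procedures at withdrawal, and Table 2 includes a tumour scan among them. Appendix 2 has symptomatic progression reported as an adverse event where it meets the definition. Only a leaver who misses that scan remains uncertain.

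One listed withdrawal reason, "Patient unable to attend two (2) or more protocol-specified study visits due to COVID-19", has no evident link to response, so it should not be counted as a source of inflation.

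**Conclusion.** The concern holds in conditional form. As written, the general route permits replacement of a patient known to have been scanned without a response, at any time, by people who can see the scan results. If replaced patients leave the 29 and replacement falls more on non-responders, the stated alpha is not protected. One selective swap is enough to exceed 0.05 (5.3% or 5.7%, against 4.7%). With assumed leaving rates of 5% to 20% among non-responders and a cap of six, type I error is 5.7% to 9.1% if no responder leaves, and 5.2% to 6.6% if responders leave half as often. The 8.2% to 11.8% for six swaps in one stage is an extreme, not an expectation.

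A reader might go further and infer that replacement as such inflates the error, or that the trial will run at about 9%. Neither follows: with equal leaving the error stays at 4.7%, and the documents give no leaving rates. The defect is that the text leaves the matter to discretion when wording could settle it.

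**What to change.** In protocol 4.1, 9.11 and 10.2 and in SAP 1.2, for the route covering consent withdrawal and other reasons only:

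1. Allow replacement only if the patient leaves before any on-treatment tumour assessment, counting the End of Treatment scan as one.
2. State that every other patient who leaves by this route keeps their place in the 10 and the 29, counted by best confirmed response and otherwise as a non-responder.
3. Record each replacement decision and its reason before further scan results are known.
4. Report ORR in all treated patients as a sensitivity analysis.
5. Say how this fits with the smoker, NICD and 7.2 replacement provisions, which this change leaves as they are.

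The cost is amendment and SAP wording, with no planned increase in sample size. The statistical price is that a patient who leaves after a first scan for an unrelated reason counts as a non-responder, although confirmation needs two on-treatment assessments. If 5% of would-be responders were lost this way (assumed), the effective rate would be 0.30 × 0.95 = 0.285, and the Step 1 formula gives power of about 76.6% instead of 80.5%.

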# Table 2:Table of Assessments (ToA)

	Screening	ning			On T	On Treatment Visits	/isits					
	Day -28 to -1	Day -1	Day 1	Day 8	Day 15	Day 22	Day 43	Day 64	Day 85	week 18 and subsequently every 6 weeks	End of Treatment	End of Study 
Visit	01	02	03	04	05	90	07	08	60	10 - n	within 7 days of	30 davs after last
Visit Window		none	əuou	none			/+	+/- 3 days				dose (+/- 3 days)
ASSESSMENT												
Signed ICF	x											
Confirm NOTCH1 LOF mutation	×											
Medical history, other known mutations, previous and	^											
ongoing metucations, termographics Cofinine test (urine based)	< ×			at the	e discretion	of the inve	stigator (on	h for natie	nts with a s	at the discretion of the investigator (only for nations with a smoking history)		Τ
Vital Signs	;	Х	X	X	X	X	X	X	X	X	X	
Height	х											
Weight		Х		х	Х	Х	Х	Х	Х	Х	Х	
Physical Examination	х										Х	
ECOG performance status		$X^3$			Х	Х	Х	Х	Х	Х	Х	
Patient-reported questionnaires (GAD-7 and PHQ-9)	Х			Х	Х	Х	Х	Х	Х	Х	Х	
Hematology	Х		Х	Х		Х	Х	Х	Х	Х	Х	
Full Blood chemistry	Х										Х	
Limited Blood chemistry & Fasting Blood Glucose		Х	Х	Х	Х	Х	Х	Х	Х	Х		
HbA1c	Х										Х	
Pregnancy test 	$X^{2a}$						$X^{2b}$	$\mathbf{X}^{2\mathrm{b}}$	$X^{2b}$	$X^{2b}$	${ m X}^{2a}$	
Radiological tumor assessment	x						Х		Х	Х	х	
Bimiralisib oral administration				Ih p	rior to brea	kfast  (fast	Ih prior to breakfast  (fasted) on Day I and 2 of every week	I and 2 of	every week			
Safety ECG	х										Х	
PK sampling 			Х	Х		Х	Х	Х				
ctDNA blood sampling	Х						Х				Х	
Dermatologic evaluation 	Х						Х	Х	Х			
Collection of archival tissue (if available)	Х											
Concomitant Medications						Every visit o	ifter the firs	st dose unti	l 30 days aj	Every visit after the first dose until 30 days after last dose		
Adverse Event monitoring						Every visit c	ufter the firs	st dose unti	l 30 days aj	Every visit after the first dose until 30 days after last dose		
Serious Adverse Event monitoring				Col	ntinuous frc	m signing a	Continuous from signing of ICF until 30 days after last dose	30 days af	ter last dos	0		

Page 16 of 81

Protocol PQR309-009	PIQUR Therapeutics AG - Confidential
Footnotes:	
1: for women of childbearing potential only	
2a: serum HCG	
2b: serum HCG or urine test	
3: ECOG may be collected anytime between day -2 and immedi	nmediately prior to first dose on day 1
4: PK sampling:	

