### 2.3.4.2 Effect of cigarette smoking on the pharmacokinetics of bimiralisib

*In vitro* experiments had identified CYP1A2 as metabolic pathway for bimiralisib[26] In order to assess the relevance of this metabolic pathway for the elimination of the compound, the PK profile after 80mg p.o. and 20mg i.v. was studied in a group of healthy male smokers (PQR309-008). If CYP1A2 was an important elimination pathway for bimiralisib in humans, smokers would eliminate the compound faster than non-smokers as CYP1A2 is induced by cigarette smoking.

Results from the PQR309-008 study fully confirmed this hypothesis [29]. Faster elimination of bimiralisib in smokers is reflected by a considerably shorter half-life of approx. 18 to 19h and the faster clearance (2 to 2.5-fold compared with non-smokers). These findings were further substantiated by concomitant administration of the CYP1A2 inhibitor fluvoxamine with bimiralisib at a separated occasion. In this setting, the half-life of bimiralisib is prolonged and the clearance substantially reduced. Taken together, these data indicate that CYP1A2 is indeed an important metabolic pathway for bimiralisib in humans leading to lower average plasma concentrations in smokers compared to non-smokers given the same [29] dose, warranting the exclusion of active smokers from the present study. Smoking status will be assessed via cotinine testing at screening. Additional cotinine tests may be administered at the discretion of the treating investigator if current smoking is suspected.

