### 4 Study design

### 4.1 Overall design

This is an open-label, single arm, two-stage study to evaluate the efficacy and safety of bimiralisib in patients with r/m HNSCC containing *NOTCH1* LOF mutations. The study will be conducted in 1 - 4 centers.

Patients will be treated with 140 mg bimiralisib p.o. once daily on two consecutive days followed by 5 days without treatment in consecutive 7-day treatment blocks. Patients will continue this iterative "2d on / 5d off" treatment scheme until unacceptable toxicity, tumor progression, patient's request for withdrawal, investigator judgment or death, whichever comes first. The bimiralisib dose may be decreased to 100 mg p.o. administered on the same dosing schedule in order to manage safety and/or tolerability (see section on dose interruptions and modifications, section 7.2). Changes in dosing schedule are not allowed.

Stage 1 of the study will enroll 10 patients. Response evaluation of Stage 1 patients will be performed in an ongoing manner (ongoing analysis, OA). If two or more patients in stage 1 show a confirmed partial or confirmed complete response, Stage 2 may enroll 19 patients. Conversely, Stage 2 may not start if only one or no patients in Stage 1 have shown a confirmed partial or confirmed complete response.

If patients withdraw consent or drop out for other reasons unrelated to safety or disease progression, they may be replaced. This includes patients who start smoking (as evidenced by cotinine test) within the first 12 weeks on bimiralisib treatment, because smoking is known to severely compromise bimiralisib exposure due to induction of CYP1A2, the main metabolizing enzyme of bimiralisib. These patients may remain on treatment but will be replaced. Patients for whom IHC analyses indicated high protein levels of NICD which are deemed incompatible with NOTCH1 loss-of-function may be replaced. In total, we anticipate up to 20% of patients to drop out, resulting in enrollment of up to 35 patients in total.

The study will end when all patients have been treated for at least 6 months or have discontinued study participation for any reason, whichever comes first.

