### 5.2 Exclusion criteria

Patients eligible for this study must not meet **any** of the following criteria:

- 1. Has an oncogenic *KRAS* mutation.
- 2. Has received any anti-cancer treatment including hormonal and investigational agents within 21 days prior to first dose of bimiralisib.
- 3. Patients who receive gamma knife radiosurgery for brain metastases or whole brain radiation are eligible if gamma knife radiosurgery was performed > 2 weeks before treatment is started or whole brain radiation was performed > 4 weeks before treatment is started, and are clinically stable.
- 4. Known hypersensitivity to any of the excipients of bimiralisib capsules.
- 5. Major surgery within 28 days prior to first dose of bimiralisib or persisting side effects that have not improved to NCI-CTCAE grade 1 or better.
- 6. Poorly controlled diabetes mellitus, steroid-induced diabetes mellitus, FPG > 150 mg/dl.
- 7. Concomitant treatment with medicinal products that increase the pH (i.e. reduce acidity) of the upper gastrointestinal tract, including, but not limited to, proton-pump inhibitors (e.g. Omeprazole), H2-antagonists (e.g. Ranitidine) and antacids is restricted. Patients may be enrolled in the study after a washout period sufficient to terminate their effect.
- 8. Active tobacco or e-cigarette smoking habit. Non-smoker status will be confirmed by cotinine test at screening in patients with a history of smoking. Additional cotinine tests may be administered at the discretion of the treating investigator if current smoking is suspected.
- 9. Patients who are on (or will require) prolonged systemic corticosteroid treatment during the study (see section 11.1.4).
- 10. Use of oral herbal preparations or medications during the study period. Patient should stop using oral herbal medications 7 days prior to the first dose of bimiralisib
- 11. Concurrent severe and/or uncontrolled medical conditions that would, in the investigator's judgment, contraindicate patient participation in the clinical study or require concomitant anti-cancer drugs (e.g., active or uncontrolled severe infection, chronic active hepatitis, immuno-compromised, acute or chronic pancreatitis, uncontrolled high blood pressure, interstitial lung disease, etc.).
- 12. Has other active malignancies that require systemic treatment.
- 13. Has a known history of HIV infection (testing not mandatory).
- 14. Any of the following cardiac abnormalities:

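### Replacing patients who start smoking depends on a cotinine test that is not scheduled after screening, so who is counted can depend on the Day 43 scan result

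*Protocol*

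**What the plan says.** **The rule.** Protocol 9.11 first allows replacement of patients who drop out for reasons other than safety or progression. It then extends this to smoking: "This includes patients who start smoking (as evidenced by cotinine test) within the first 12 weeks on bimiralisib treatment". The consequence is firm: "These patients may remain on treatment but will be replaced". Section 4.1 has the same rule and gives the reason, that "smoking is known to severely compromise bimiralisib exposure due to induction of CYP1A2". Section 2.3.4.2 puts clearance in smokers at 2 to 2.5 times that in non-smokers.

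**The measurement.** Section 5.2, criterion 8, provides a test at entry: "Non-smoker status will be confirmed by cotinine test at screening in patients with a history of smoking". After entry it says only: "Additional cotinine tests may be administered at the discretion of the treating investigator if current smoking is suspected". Table 2 agrees. Cotinine has a scheduled mark at screening and is otherwise discretionary, limited to patients with a smoking history. No on-treatment visit, frequency or objective trigger is given.

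**The setting.** The trial is open-label and single-arm (4.1). Scans are read locally, with the first two on-treatment assessments at Day 43 and Day 85, each ±3 days (9.3). Efficacy is analysed on the per-protocol set, PPS (10.4.1). Its exclusions are left to the data handling plan and the SAP (10.3.2); the SAP text supplied contains only the hypotheses and the sample size.

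**The concern.** Replacement is compulsory once a positive test exists, but obtaining the test is optional. The person who decides whether to test can already know the Day 43 result, which falls well inside the 12-week window (12 × 7 = 84 days). The protocol itself links smoking to low exposure, so a patient whose tumor is not shrinking is a natural one to suspect, while a responding patient gives no such prompt. No misconduct is needed for testing to follow outcome.

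If it does, non-responding smokers leave the counted set and responding smokers stay. The ORR and the chance of passing either stage of the design then rise. If nobody tests, under-exposed smokers stay in and dilute the ORR. In both cases the result depends partly on testing behaviour.

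**Working it through.** **Inputs from the documents.** Null ORR 10%, alternative 30%; 10 patients in stage 1, stop at 0 or 1 response; 29 in total, reject at 6 or more (Protocol 10.2, SAP 1.2). Up to 35 enrolled, so 35 − 29 = 6 replacements for all causes together.

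**Step 1: the plan's own design.** The rejection probability at ORR p is the sum over x = 2 to 10 of P(X₁ = x) × P(X₂ ≥ 6 − x), with X₁ ~ Bin(10, p) and X₂ ~ Bin(19, p). This gives 0.047 at 10% and 0.805 at 30%. The chance of opening stage 2 at 10% is 1 − 0.9¹⁰ − 10 × 0.1 × 0.9⁹ = 0.264. The stated design reproduces.

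**Step 2: assumptions for the illustration.** A share s of patients resumes smoking. Non-smokers have ORR p = 10% and smokers have ORR q. Every non-responding smoker is tested and replaced; no responding smoker is. None of s, q or the testing pattern is in the documents.

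**Step 3: counted ORR with no ceiling on replacements.** It is [(1 − s)p + sq] / [(1 − s) + sq].

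- q = 10%: 0.1/0.91 = 11.0%, 0.1/0.82 = 12.2%, 0.1/0.73 = 13.7% for s = 10%, 20%, 30%.
- q = 5%: 0.095/0.905 = 10.5%, 0.090/0.810 = 11.1%, 0.085/0.715 = 11.9%.
- q = 0%: (1 − s)p/(1 − s) = 10% for every s.

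**Step 4: apply the ceiling.** With q = 10% and no ceiling, the mean number replaced per 29 counted is 29 × 0.9s/(1 − 0.9s), that is 2.9, 6.4 and 10.7. The last two exceed 6. So I followed patients one at a time. Each is a counted responder with probability (1 − s)p + sq. With probability s(1 − q) the patient is replaced if fewer than 6 have been replaced, and otherwise counted as a non-responder. The remainder are counted non-responders. The trial stops at 10 counted with 0 or 1 response and rejects at 29 counted with 6 or more.

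Probability of rejecting the null (4.7% with no selective replacement):

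| s | q = 10%, no ceiling | q = 10%, at most 6 | q = 5%, no ceiling | q = 5%, at most 6 | q = 0%, no ceiling |
|---|---|---|---|---|---|
| 10% | 6.8% | 6.8% | 5.7% | 5.7% | 4.7% |
| 20% | 10.1% | 9.1% | 7.1% | 6.2% | 4.7% |
| 30% | 15.1% | 10.5% | 9.2% | 5.8% | 4.7% |

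The ceiling figures are exact to rounding; a simulation of the same process agreed to about 0.1 percentage points. With q = 0% the ceiling cannot raise the figure, because smokers beyond the sixth stay in as non-responders. With q = 10% and the ceiling, the chance of opening stage 2 is about 30%, 35% and 40%, against 26%.

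**Step 5: the opposite failure.** Suppose nobody tests, 10% of counted patients are undetected smokers with ORR 0 to 15%, and the others have ORR 30%. The overall ORR is 0.27 + 0.1q = 27.0% to 28.5%, and power falls from 0.805 to 0.72–0.77.

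**The case against.** **Discretion is bounded.** Testing needs suspicion and, in Table 2, a smoking history. Active smokers are excluded, and patients with a smoking history are tested at screening. This should keep numbers down, but suspicion is undefined and is formed by someone who may know the scan.

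**Section 9.11 already excludes progression.** The smoking sentence falls under a rule limited to reasons other than safety or progression. On a plain reading, a patient who progressed at Day 43 cannot have the slot freed by a later cotinine test. This narrows the route, though no text says it in terms. It leaves patients who have neither progressed nor responded at Day 43. Some of them may respond later, and no response can be confirmed before about Day 85, so not every eventual non-responder is identifiable inside the window. The illustration assumes that all are, and so overstates the effect.

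**Smokers may not respond as well as others.** The inflation comes only from responding smokers who are kept. If under-exposure removes response altogether, it vanishes. This stands, and is why q is varied.

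**Removal from the PPS is not established.** A reader might infer that replaced smokers leave the efficacy analysis. The supplied text does not say so, and the data handling plan is not available. That silence is part of the gap, not evidence of bias.

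**Scheduling tests through Day 85 would not cure it.** Patients who progress at Day 43 leave treatment and miss later tests, while responders take them all. Day 85 also sits at the edge of the window.

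**Conclusion.** The point holds as an ascertainment gap: the evidence for a compulsory replacement rule is collected at the discretion of an unblinded investigator, partly after the first response result. If testing is fully selective at a true ORR of 10%, the type I error rises from 4.7% to about 7%, 9% or 10% for 10%, 20% or 30% resuming smoking, with at most 6 replacements and smokers responding as well as others. It rises less if their ORR is 5%, and not at all if it is 0%. These are illustrations, because the documents give no rate of smoking or testing.

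A reader might infer a false-positive rate near 15%. That figure needs 30% smoking, unlimited replacement and an unreduced smoker ORR together. It implies about 11 replaced smokers, against 6 replacements for all causes in the plan. Nor do the documents show that the sample size is wrong: 10 and 29 reproduce, and they keep their stated properties if replacement is unrelated to response. Clarification is worthwhile because the remedy is cheap.

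**What to change.** 1. In Protocol 4.1 and 9.11, use one rule: a positive cotinine test leads to replacement only if the urine was collected before the patient's first on-treatment scan result was known. Later positives are recorded, and the patient stays in the counted set.
2. In Table 2, schedule the existing site urine test at Day 22 and at Day 43, before the scan is read, for patients with a smoking history.
3. Report ORR in all treated patients (the safety set) alongside the PPS, and state in the SAP whether replaced smokers leave the PPS.

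**Cost.** Two urine tests per patient with a smoking history at existing visits, a wording change and one more summary. The rule is not free: it shortens the period in which smoking can lead to replacement from 12 weeks to about six. Smokers first detected after the Day 43 result stay in the count. This slightly dilutes the ORR and costs some power, but the error is in the conservative direction. A never-smoker who starts smoking would still have no scheduled test.
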